## **10.3. Cognitive Outcomes**

The secondary endpoints consist of performance differences in the FOME and the RBMT-C between subjects receiving glulisine and those receiving saline. These differences will be assessed using normal mixed-effects regression accounting for period and the treatment-period interaction as well as subject age and sex.

## **10.4. Study Power**

Power analysis for the primary endpoint (incidence of adverse events) is simplified to a comparison of paired means. The following table presents power estimates for a variety of assumptions. Assumptions common to all scenarios are a sample size of 12 and an alpha of 0.05. The difference column corresponds to the difference in number of adverse events between the treatment and the placebo. Although only half of these probable scenarios are adequately powered, such a result is acceptable for a pilot study such as this.

| Difference | St. Dev. | Power |
|-------------------|-----------------|--------------|
| 1.5               | 1.0             | 0.997        |
| 1.5               | 1.5             | 0.883        |
| 1.5               | 2.0             | 0.658        |
| 2.0               | 1.0             | 1.000        |
| 2.0               | 1.5             | 0.987        |
| 2.0               | 2.0             | 0.883        |

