## PROTOCOL SYNOPSIS

|   |   |  |  |  |  |  |
|---|---|--|--|--|--|--|
| PROTOCOL TITLE  | A Double-Blind, Placebo-Controlled Pilot Investigation of the Safety of Intranasal Glulisine in Down Syndrome (DS)  |  |  |  |  |  |
| SHORT TITLE   | Down IN Insulin Study   |  |  |  |  |  |
| STUDY PHASE   | Pilot   |  |  |  |  |  |
| STUDY OBJECTIVES AND PURPOSE  |   |  |  |  |  |  |
| 
Study Purpose
 
The purpose of this study is to provide safety evidence to support the development of intranasal (IN) glulisine as a treatment option for cognitive impairment in DS.
                            |   |  |  |  |  |  |
| 
Primary Objective
 
 
• To demonstrate the safety of IN glulisine in DS.
 
• To demonstrate the feasibility of performing a cognitive performance battery in DS.
 
 |   |  |  |  |  |  |
| 
Secondary Objective (s)
 
 
• To estimate the effects of IN glulisine on cognition and memory in DS.
 
  |   |  |  |  |  |  |
| STUDY DESIGN  |   |  |  |  |  |  |
| Study Type  | Safety  |  |  |  |  |  |
| Control Type  | Placebo   |  |  |  |  |  |
| Study Indication Type   | Treatment   |  |  |  |  |  |
| Blinding Schema   | Double-Blind  |  |  |  |  |  |
| Device  | Pressurized Olfactory Delivery (POD) device   |  |  |  |  |  |
| Study Design  | 
This study is a single center, randomized, double-blind, placebo-controlled, cross-over pilot study designed to assess the safety of intranasally (IN) delivered glulisine versus placebo in patients with DS. Subjects will be randomized into this cross-over study and within subject comparisons conducted between single treatment of intranasal insulin glulisine and single treatment of intranasal placebo. All subjects will also receive a single treatment of placebo prior to randomization to ensure adherence to study procedures.
 |  |  |  |  |  |
| Planned Duration of Subject Participation   | 
The duration of study participation for each subject is anticipated to be between 6-7 weeks.
   |  |  |  |  |  |
| OUTCOMES  | Primary-Safety  | 
 
• Number of related adverse and/or serious events
 
• Number of any adverse and/or serious events
 
 |  |  |  |  |

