To test the hypothesis regarding the acute safety and efficacy of rapid acting (RA) insulin glulisine in AD, our group performed a double blinded, randomized, placebo-controlled, cross-over study in 9 mild-moderate ApoE4+ AD subjects. Glulisine is a rapidly absorbed insulin analogue lacking the zinc ingredient commonly found in insulin formulations, and may hypothetically be a safer, better tolerated insulin considering findings that zinc-containing compounds may be toxic to olfactory neurons [50, 51]. The study drug was administered intranasally using the LMA Mucosal Atomization Device (MAD). Treated subjects made fewer Trails B errors relative to controls. Otherwise, there were no significant difference between intranasal glulisine and placebo for cognitive tests of learning/memory, attention/executive function, language, or visuospatial function. Fingerstick glucose was not impacted by IN glulisine, but the drug resulted in a 19% decrease in insulin levels compared to baseline. The findings indicated that mild-moderate ApoE4+ AD patients were unresponsive to acute IN glulisine, but that the drug was safe and well-tolerated.

In the current study, we aim to demonstrate the safety of IN RA insulin glulisine in the DS population with a double blinded, randomized, placebo-controlled, cross-over study design. This investigation will enroll DS subjects with a high probability of elevated plaque burden, aged  $\geq 35$ , who may or may not be suffering from dementia. Recognizing the logistical limitations of positioning and administering study drug with the LMA MAD device, we will be using the Impel intranasal device (see description below), which would be expected to more efficiently deliver study drug to the target region.

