### **3. OBJECTIVES AND ENDPOINTS**

#### **3.1. Primary Objectives**

To demonstrate the safety of IN glulisine in DS.

To demonstrate the feasibility of performing a cognitive performance battery in DS.

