## **10. DATA ANALYSIS AND STATISTICAL CONSIDERATIONS**

### **10.1. Statistical Analysis**

All primary and secondary endpoints will be summarized within strata defined by treatment and study period.

Treatment effects on both primary and secondary endpoints will be assessed using common statistical methodology for crossover trials. Continuous outcomes, such as the FOME and the RBMT-C, and count outcomes, such as adverse event incidence, will be analyzed using a mixed-effects linear model to account for period effects and patient characteristics such as age and sex. Plots of the observed effects will be constructed to aid with interpretation.

All statistical analyses will be completed using SAS® software. Visual representations of the data will be constructed using the package ‘ggplot2’ in R [63, 64].

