## **10.2. Safety Outcomes**

The primary endpoint is defined as the ‘incidence of any or related adverse and/or serious events of intranasal glulisine versus placebo.’ The difference in incidence of adverse events between subjects receiving glulisine and those receiving saline will be modeled in terms of rates using a mixed-effects Poisson regression model accounting for period and the treatment-period interaction as well as subject age and sex.

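### Sections 10.1 and 10.2 name different models for the primary AE counts, and two of the six power rows in 10.4 cannot occur under the Poisson model of 10.2

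*Combined protocol and SAP*

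**What the plan says.** Section 10.1 states that "count outcomes, such as adverse event incidence, will be analyzed using a mixed-effects linear model", with period and patient characteristics as adjustments. Section 10.2 then takes the primary endpoint, AE incidence on glulisine versus placebo, and says it will be "modeled in terms of rates using a mixed-effects Poisson regression model", with period, treatment-period interaction, age and sex. No sentence says which section prevails.

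Section 10.4 uses a third approach and discloses it: "Power analysis for the primary endpoint (incidence of adverse events) is simplified to a comparison of paired means". On the effect size it says: "The difference column corresponds to the difference in number of adverse events between the treatment and the placebo". All scenarios use 12 subjects and alpha 0.05. The differences are 1.5 and 2.0, each with a St. Dev. of 1.0, 1.5 and 2.0. The section concludes: "Although only half of these probable scenarios are adequately powered, such a result is acceptable for a pilot study such as this". It does not say which standard deviation the column holds, whether the test is two-sided, or what power counts as adequate.

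The first primary objective in 3.1 reads "To demonstrate the safety of IN glulisine in DS", and the introduction says "we aim to demonstrate the safety of IN RA insulin glulisine in the DS population". The study purpose in the synopsis is more modest: to "provide safety evidence to support the development of intranasal (IN) glulisine". No margin or acceptable rate ratio is given anywhere.

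**The concern.** The two models differ in more than name. A linear model estimates a difference in mean counts with a free residual variance. A Poisson model estimates a rate ratio and ties the variance to the mean. With 12 subjects and small counts they can give different p-values and intervals, and the text as written leaves the choice open until the data are seen.

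The power table inherits the problem. A paired-t calculation lets the difference and its SD be chosen freely. A Poisson model does not: a large difference in counts forces a minimum spread. Rows that break this constraint cannot describe data from the model in 10.2, so they give no support for n=12 under that model.

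The third issue is separate. The table shows nothing smaller than 1.5 extra AEs per subject after a single dose, while the objective is worded as a demonstration of safety.

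**Working it through.** **Reproducing the table.** Inputs from 10.4: n=12, alpha 0.05, difference d, standard deviation s. For a two-sided paired t-test, df = 11, the critical value is 2.201 and the noncentrality is (d/s)√12. For d=1.5, s=1.5 this is 1 × 3.464 = 3.464, giving power 0.883. All six rows match to three decimals (table below). A normal approximation (0.934 where the table has 0.883), a one-sided t (0.945) and a two-sample t with 12 per arm (0.649) do not match. The column therefore acts as the SD of the within-subject difference.

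**The constraint from 10.2.** Let the two counts of a subject be Poisson given a shared subject effect, with means m_G (glulisine) and m_P (placebo). Then

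Var(Y_G − Y_P) = (m_G + m_P) + (a term ≥ 0 from between-subject variation) ≥ m_G + m_P.

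With m_G = m_P + d this gives s² ≥ 2m_P + d, so m_P ≤ (s² − d)/2. Since m_P cannot be negative, s must be at least √d: 1.22 for d=1.5 and 1.41 for d=2.0. The implied rate ratio is at least 1 + 2d/(s² − d).

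| d | s | Power in 10.4 | Paired t, recomputed | Largest m_P | Smallest rate ratio | Exact Poisson power |
|---|---|---|---|---|---|---|
| 1.5 | 1.0 | 0.997 | 0.997 | (1−1.5)/2 = −0.25 | impossible | – |
| 1.5 | 1.5 | 0.883 | 0.883 | (2.25−1.5)/2 = 0.375 | 1.875/0.375 = 5.0 | 0.935 |
| 1.5 | 2.0 | 0.658 | 0.658 | (4−1.5)/2 = 1.25 | 2.75/1.25 = 2.2 | 0.706 |
| 2.0 | 1.0 | 1.000 | 1.000 | (1−2)/2 = −0.50 | impossible | – |
| 2.0 | 1.5 | 0.987 | 0.987 | (2.25−2)/2 = 0.125 | 2.125/0.125 = 17 | 0.999 |
| 2.0 | 2.0 | 0.883 | 0.883 | (4−2)/2 = 1.0 | 3.0/1.0 = 3.0 | 0.931 |

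The last column is a two-sided exact conditional test on total counts 12m_G and 12m_P at the largest m_P. It omits random effects, covariates and the interaction. In the four rows that fit, it is somewhat above the printed power.

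**The adequacy statement.** Powers of at least 0.90 are 0.997, 1.000 and 0.987: three of six, which agrees with the text. At 0.80 the count is five of six. The text therefore implies a 0.90 threshold, and two of the three rows that meet it are the impossible ones.

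**Differences the table does not show.** Paired-t power, n=12, at SD 1.5 and 2.0:
- difference 1.0: 0.56 and 0.35
- difference 0.5: 0.18 and 0.12
- difference 0.25: 0.08 and 0.07

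**Illustration on the rate scale.** The documents give no placebo AE rate. At assumed placebo means of 0.5, 1.0 and 1.5 AEs per dose, exact Poisson power for a true doubling is 0.22, 0.45 and 0.65. Equal totals of 12 AEs on each treatment (1.0 per dose) leave a 95% interval for the rate ratio of 0.41 to 2.43.

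**The case against.** The strongest reply is that no printed number is wrong. The powers are right, the simplification is stated, limited power is accepted for a pilot, and where the table fits the Poisson model it is slightly conservative. All of that stands. A reader might infer from the mismatch that the power is overstated throughout; the four feasible rows show the opposite.

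It can also be said that 10.1 is a general paragraph and that 10.2, being specific to the endpoint, naturally governs. That is the likely intent, and it makes the correction easy. But 10.1 names AE incidence explicitly as an outcome for the linear model, so the wording does conflict.

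The SD 1.0 rows are admissible under the paired-means method that 10.4 says it uses, or under an under-dispersed count model. True, but neither is the model that 10.2 specifies for the primary endpoint.

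Finally, a reader might infer that the plan will treat a non-significant AE difference as proof of safety, or that the model conflict and the large rate ratios are what prevent such proof. The documents support neither. No section states that rule, the synopsis describes a pilot that gathers safety evidence, and 10.1 also plans summaries by treatment and period. The limit comes from testing a difference without a margin in 12 subjects, and it would hold under either model and any power table.

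**Conclusion.** The point holds in three limited parts.

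First, 10.1 and 10.2 give conflicting models for the primary endpoint.

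Second, two of the six power rows cannot arise under 10.2, although they are described as probable, and they supply two of the three rows behind the adequacy statement. The remaining four support n=12 only for rate ratios of at least 5.0, 2.2, 17 and 3.0. The smallest of these, 2.2, carries a stated power of only 0.658. It is the smallest ratio the table implies, not a minimum detectable ratio, which would depend on a placebo rate that the documents do not give.

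Third, and independently, a non-significant difference at n=12 could not by itself demonstrate safety, and no other criterion is stated.

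The variance bound assumes that the St. Dev. column is the SD of the paired difference, as the reproduction supports, and that counts are Poisson given the subject effect. The doubling figures of about 0.22 to 0.65 rest on assumed placebo means of 0.5 to 1.5. None of this argues for a different sample size. The corrections are worth making because they settle the primary analysis rule at almost no cost.

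**What to change.** Keep n=12.

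- **10.1:** remove AE counts from the linear-model sentence, so that 10.2 governs the primary endpoint.
- **10.4:** label St. Dev. as the SD of the within-subject difference and name the adequacy threshold. Replace the two SD 1.0 rows with scenarios given as placebo and glulisine means, labelled as a simplified Poisson calculation without random effects, covariates or interaction. Add smaller differences. Example rows at an assumed placebo mean of 0.5: glulisine means of 0.75, 1.0 and 1.5 give exact power of 0.08, 0.22 and 0.63.
- **10.2:** report the AE rate ratio and rate difference with 95% confidence intervals, and state that a non-significant difference will not be interpreted as demonstrated safety.
- **Optional, in 3.1, the synopsis objective and the aim in section 1:** bring the verb into line with the study purpose in the synopsis, for example by providing evidence on safety.

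The cost is a few sentences and a short recalculation, with no change to sample size, visits or procedures. The downside is that the stated power looks less favourable and, if the optional change is made, the objective is more modest.

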## **11. STUDY CONDUCT CONSIDERATIONS**

### **11.1. Regulatory and Ethical Considerations**

The study will be conducted in accordance with GCP guidelines. Subject privacy requirements will be observed as well as the fundamental concepts of the Declaration of Helsinki (E.G. IRB approval of the study, obtaining informed consent from all subjects and meeting all reporting requirements).

### **11.2. Quality Assurance**

In the event of a regulatory agency audit or inspection, site will allow the auditor/inspector access to all records documented and facilities utilized in conducting the study. Site will also make accommodations (e.g. time, schedule) to discuss findings, concerns, and questions with auditor/inspector.

### **11.3. Study Closure**

Upon completion of all subject visits, data entry and analysis, investigator will inform local IRB of study closure.

### **11.4. Records Retention**

All site records will be maintained and stored in a safe and secure location for a minimum of 15 years post study completion.

### **11.5. Provision of Study Results and Information to Investigators**

Study results will be made available by the study statistician once analysis (Interim Analysis) is complete. Study Staff will not be unblinded in regards to individual subjects randomization status until after the database is locked.

### **11.6. Data Management**

Data collection/reporting tools will be developed internally (i.e. CRFs and source documents). Data collected and stored electronically will remain confidential and secure (e.g. secured server, encrypted data, and password protected file).

